### Section 6.3. Dosage and administration of study vaccines

**Table 10 Dosage and administration**

Type of contact and time point	Volume to be administered	Study group	Treatment name	Route 	Site 	Side 
Visit 2 ( <del>Day 0</del> Month 3-9)	0.5 mL	dTpa Group and Control Group	Infanrix hexa	IM	‡Thigh or Deltoid 	R
Visit 2 ( <del>Day 30</del> Month 3-9)	0.5 mL	dTpa Group and Control Group	Prevenar 13	IM	‡Thigh or Deltoid 	L

Intramuscular (IM)

The vaccines should be administered in the thigh or deltoid, according to the national recommendations

Thigh (T)

Right (R), Left (L)

### 6.6. Warnings and precautions

The information below presents, in addition to the contraindications in Section 6.5, warnings and precautions to administration of *Infanrix hexa*.

- If any of the following events are known to have occurred in temporal relation to receipt of pertussis-containing vaccine, the decision to give further doses of pertussis-containing vaccines should be carefully considered:
  - Collapse or shock-like state (hypotonic-hyporesponsiveness episode [**HHE**]) within 48 hours of vaccination.
- Increased reporting rates of convulsions (with or without fever) and ~~hypotonic hyporesponsive episode (HHE)~~ were observed with concomitant administration of *Infanrix hexa* and *Prevenar 13*.

Warnings and Precautions for the use of *Prevenar13*:

- Increased reporting rates of convulsions (with or without fever) and ~~hypotonic hyporesponsive episode (HHE)~~ were observed with concomitant administration of *Infanrix hexa* and *Prevenar 13*.

**6.7.1. Recording of concomitant medications/products and concomitant vaccinations**

- All concomitant medications/products, except vitamins and dietary supplements, administered during the period starting from the administration of the dose of study vaccines (Visit 2) and ending at ~~the last study visit (Visit 3 (Day 0 to Day 30))~~.
- Any concomitant vaccination administered in the period starting from the administration of the dose of study vaccines (Visit 2) and ending at the ~~last study visit 3 (Day 0 to Day 30) (Visit 3)~~.

**8.2.1. Time period for detecting and recording adverse events and serious adverse events**

The time period for collecting and recording SAEs will begin at the receipt of study vaccines and will end ~~30 days following administration of the dose of study vaccines~~ **when the subject is discharged from the study**. See Section 8.3 for instructions on reporting of SAEs.

All AEs/SAEs leading to withdrawal from the study will be collected and recorded from the time **the subjects have been enrolled in the study** ~~of the receipt of study vaccines~~.

**Table 13 Reporting periods for collecting safety information**

Event	V 1	V2	4 d post V2	31 d post-V2	V3	Phone contact * Study Conclusion
Age of subject	9 months	11 12-18 months			12 13-19 months	18 months †
Timepoint	Month -9 to -2	M-3-9 Day 0	Day 3	Day 30	M-4-10 Day 30	Day 0 to Month 7
AEs/SAEs leading to withdrawal from the study						
SAEs						

\* i.e., consent obtained for vaccination. Pre-V: pre-vaccination; V: Visit; Post-V: post-visit; D: Day, M: Month;

\* **For Czech Republic, the phone call at 18 months may be replaced by a clinic visit if deemed preferable by the study team.**

† Neurodevelopmental status will be recorded at 9 months and 18 months of age. It is encouraged that subjects who are getting vaccinated at 18 months of age at Visit 2 or coming for Visit 3, complete their ASQ-3 during their visit to the study centre. In case subjects complete Visit 3 before 18 months of age, the study staff will contact the parents/LAR(s) via phone and conduct an interview to complete the child's ASQ-3 at 18 months of age.

If the subject is referred to a developmental specialist for formal assessment, then this information needs to be recorded in the eCRF. Also, the overall assessment of delay by the specialist should be recorded in the eCRF.

**8.2.3.2.1. Assessment of intensity**

The maximum intensity of fever (*oral, axillary or tympanic route*) will be scored at GSK Biologicals as follows:

**8.2.3.2.2. Assessment of causality**

The investigator will also consult the IB and/or *PI Prescribing Information* for marketed products to determine his/her assessment.

10.3. Determination of sample size

Table 17 Reference values (booster phase)

Reference Study	Observed seroprotection rates		Booster response for Pertussis antigens			Observed Seroprotection rates				
	D	T	PT	FHA	PRN	PRP	HBs	Anti-IPV1	Anti-IPV2	Anti-IPV3
217744/054	100.0% [97.9,100.0]	100.0% [97.9,100.0]	100.0% [97.8,100.0]	100.0% [97.8,100.0]	100.0% [97.9,100.0]	100.0% [97.9,100.0]	98.9 (95.9,99.9)	100.0% [97.6,100.0]	100.0% [97.5,100.0]	100.0% [97.5,100.0]

217744/054: Group receiving DTPa-HBV-IPV/Hib according to 3,5,11 schedule in Italy and Germany

**10.4.2. Total vaccinated cohort**

The ~~Total Vaccinated cohort (TVC)~~ will include all vaccinated subjects for whom data are available.

**10.4.3. According-to-protocol cohort for analysis of safety**

The ATP cohort for analysis of safety will include all subjects from the TVC who complied with the vaccine administration:

- who have received **all** ~~at least one~~ vaccine doses in the primary study DTPA (BOOSTRIX)-048 PRI.
- who have received the booster dose *of study vaccines* in the current study.

**10.4.4. According-to-protocol cohort for analysis of immunogenicity**

The ATP cohort for analysis of immunogenicity will include all evaluable subjects from the ATP cohort for analysis of safety:

- Who received all ~~three~~ doses of vaccine in the primary study ~~201330~~ 201334 [DTPA (BOOSTRIX)-048 PRI].

**10.6. analysis of demographics**

Demographic characteristics (age in months, race, length [cm], weight [kg], head circumference [cm]), cohort description and withdrawal status will be summarised by group using descriptive statistics:

- Frequency tables will be generated for categorical variables such as race, *country or primary vaccination schedule*;

**10.7. analysis of immunogenicity**

~~For serology results one month after the booster dose:~~

- The booster response rates to PT, FHA and PRN (with exact 95% CI) *one month after the booster dose* will be calculated.

*The above summaries will be provided by country or primary vaccination schedule for countries involving more than 50 subjects.*

- The distribution of antibody concentrations/titres for each antigen will be displayed using reverse cumulative distribution curves (RCCs).
- The distribution of antibody concentrations or titres of each antigen will be tabulated.

~~The above summaries will be stratified based on country and primary vaccination schedule conducted as exploratory analysis.~~

**10.8. Analysis of safety**

The percentage of subjects reporting each individual solicited local and general symptom during the 4-day (Day 0-Day 3) solicited follow-up period will be tabulated after the

vaccine dose and overall, with exact 95% CI [Clopper, 1934]. The same calculations will be done for each individual solicited symptom rated as grade 3 in intensity and for each individual solicited symptom assessed as causally related to vaccination.

### **11.5. Posting of information on publicly available clinical trial registers and publication policy**

*GSK assures that the key design elements of this protocol will be posted on the GSK website and in publicly accessible database(s) such as clinicaltrials.gov, in compliance with the current regulations.*

*GSK also assures that results of this study will be posted on the GSK website and in publicly accessible regulatory registry(ies) within the required time-frame, in compliance with the current regulations. The minimal requirement is to have primary endpoint summary results disclosed at latest 12 months post primary completion date (PCD) and to have secondary endpoint disclosed at latest 12 months after the last subject last visit (LSLV) as described in the protocol.*

*As per EU regulation, summaries of the results of GSK interventional studies (phase I-IV) in paediatric population conducted in at least one EU member state will be posted on publicly available EMA registers within 6 months of EoS (as defined in the protocol) in the concerned EU member state. However, where, for scientific reasons detailed in the protocol, it is not possible to submit a summary of the results within 6 months in the concerned EU member state, the summary of results shall be submitted as soon as it is available. In this case, the protocol shall specify when the results are going to be submitted, together with a justification.*

*GSK also aims to publish the results of these studies in searchable, peer reviewed scientific literature and follows the guidance from the International Committee of Medical Journal Editors.*

~~Study information from this protocol will be posted on publicly available clinical trial registers before enrollment of subjects begins.~~

~~Summaries of the results of GSK interventional studies (phase I-IV) are posted on publicly available results registers within six months of the primary completion date for studies of authorised vaccines and 18 months for studies of non-authorised vaccines.~~

~~GSK also aims to publish the results of these studies in the searchable, peer reviewed scientific literature. Manuscripts are submitted for publication within 24 months of the last subject's last visit. At the time of publication, this protocol will be fully disclosed.~~

SBIR	GSK Biological's Internet Randomisation System
SD	Standard Deviation
SR	Study Report
TFL	Tables Figures and Listings
ToC	Table of Content
UL	Upper Limit of the confidence interval
WBR	Web-based Randomisation

1. DOCUMENT HISTORY

Date	Description	Protocol Version
22 MAR 2019	First version	Final: 12 DEC 2016

2. STUDY DESIGN OBJECTIVES/ENDPOINTS

N: Maximum Number of subjects planned to be enrolled; Mo: Age in Months

*The neurodevelopmental status will be recorded when the subject is 9 months and 18 months of age. It is encouraged that subjects who are getting vaccinated at 18 months of age at Visit 2 or coming for Visit 3, complete their ASQ-3 during their visit to the study centre. In case subjects complete Visit 3 before 18 months of age, the study staff will contact the parents/LAR(s) via phone and conduct an interview to complete the child's ASQ-3 at 18 months of age. For Czech Republic, the phone call at 18 months may be replaced by a clinic visit if deemed preferable by the study team.

** Subjects have received either 2 or 3 doses of Infanrix hexa and Prevnar during the course of the study DTPA (Boostrix)-048, depending on the national/ local routine immunization schedule.

Refer to Section 5.6.2.13 of the protocol for further details.

Pre-Bst: Blood sample to be collected before the booster dose.

Post-Bst: Blood sample to be collected one month after the booster dose.

Protocol waivers or exemptions are not allowed with the exception of immediate safety concerns. Therefore, adherence to the study design requirements, including those specified in the outline of study procedures (Section 5.5 of the protocol), are essential and required for study conduct.

- Experimental design: Phase IV, open-label, non-randomised, multi-centric, multi-country study with two parallel groups.

- Duration of the study: The intended duration of the study, is approximately 9 to 10 months, per subject.
 - Epoch 001: Booster phase starting at Visit 1 (9 months of age) and ending at telephone contact or at Visit 3 (18 or 19 months of age), depending on the time of vaccination. End of Study (EoS): Last testing results released of samples collected at Visit 3.
- Study groups: The study groups and epoch foreseen in the study are presented in [Table 1](#).
 - dTpa Group: This group will consist of infants born to mothers belonging to the dTpa Group in study 116945 [DTPA (BOOSTRIX)-047] i.e., mothers who received a single dose of *Boostrix* during pregnancy and a dose of placebo immediately post-delivery and infants who received full primary vaccination course as per protocol requirement in the study 201330 [DTPA (BOOSTRIX)-048 PRI]. All subjects in this group will receive a booster dose of *Infanrix hexa* co-administered with Prevenar 13 according to the routine national/ local immunization schedule or as specified in the SPM.
 - Control Group: This group will consist of infants born to mothers belonging to the Control group in study 116945 [DTPA (BOOSTRIX)-047] i.e., mothers who received a single dose of placebo during pregnancy and a dose of *Boostrix* immediately post-delivery and infants who received full primary vaccination course as per protocol requirement in the study 201330 [DTPA (BOOSTRIX)-048 PRI]. All subjects in this group will receive a booster dose of *Infanrix hexa* co-administered with Prevenar 13 according to the routine national/ local immunization schedule or as specified in the SPM.

Table 1 Study groups and epoch foreseen in the study

Study groups	Number of subjects*	Age (Min/Max)**	Epoch
			Epoch 001
dTpa Group	340	11 months-19 months	x
Control Group	340	11 months-19 months	x

*Maximum number of subjects

**Age at the time of vaccination depending on routine national/ local immunization schedule or as specified in the SPM

The study groups and treatment foreseen in the study is presented in [Table 2](#).

Table 2 Study groups and treatment foreseen in the study

Treatment name	Vaccine name	Study Groups	
		dTpa Group	Control Group
Infanrix hexa	DTPa-HBV-IPV	x	x
	Hib	x	x
Prevenar 13	Prevenar 13	x	x

- Control: uncontrolled (No active control or placebo. All subjects will receive the same vaccine)
- Vaccination schedule: All subjects will receive a booster dose of *Infanrix hexa* co-administered with *Prevenar 13* between 11-18 months of age according to the routine national/ local immunization schedule or as specified in the SPM.
- Treatment allocation: Non-randomised. All subjects will receive a booster dose of *Infanrix hexa* co-administered with *Prevenar 13*.
- Blinding: Open-label. Note: The study personnel operating with the GSK Biologicals' central Randomisation System on Internet (SBIR) and the site staff will remain blinded towards the treatment allocation of the mother in study 116945 [DTPA (BOOSTRIX)-047].

The blinding of study epoch is presented in [Table 3](#).

Table 3 Blinding of study epoch

Study Epoch	Blinding
Epoch 001	open

- Sampling schedule: Blood samples will be drawn from all subjects at the following time points:
 - Pre-Bst: Before the booster dose administration, a volume of approximately 5 mL of whole blood (to provide approximately 1.7 mL of serum) will be collected.
 - Post-Bst: One month after the booster dose, approximately 5 mL of whole blood (to provide approximately 1.7 mL of serum) will be collected.
- Type of study: extension of other protocol(s) 116945 [DTPA (BOOSTRIX)-047] and 201330 [DTPA (BOOSTRIX)-048 PRI].
- Data collection: Electronic Case Report Form (eCRF).
- Safety monitoring: An independent data monitoring committee (IDMC) (including paediatricians and a statistician) will be put in place to oversee the safety aspects including neurodevelopmental status of infants born to mothers vaccinated with *Boostrix* during pregnancy or immediately post-delivery in the clinical study i.e., each SAE/incidence of grade 3 local and general solicited AEs, unsolicited AEs will be reviewed by this committee as per approved IDMC charter.

3. OBJECTIVES

3.1. Primary objective

- To assess the immunological response to *Infanrix hexa* in terms of seroprotection status for diphtheria, tetanus, hepatitis B, poliovirus and Hib antigens, and in terms of booster response for the pertussis antigens, one month after the booster dose in infants born to mothers vaccinated with *Boostrix* during pregnancy or immediately post-delivery.

Refer to Section 3.3 for the definition of the primary endpoint.

3.2. Secondary objectives

- To assess the persistence of antibodies to all vaccine antigens before the booster dose in infants born to mothers vaccinated with *Boostrix* during pregnancy or immediately post-delivery.
- To assess the immunological response to *Infanrix hexa* and *Prevenar 13* in terms of antibody concentrations or titres against all antigens, one month after the booster dose in infants born to mothers vaccinated with *Boostrix* during pregnancy or immediately post-delivery.
- To assess the immunological response to *Infanrix hexa* in terms of seropositivity rates against pertussis antigens, one month after the booster dose in infants born to mothers vaccinated with *Boostrix* during pregnancy or immediately post-delivery.
- To assess the safety and reactogenicity of *Infanrix hexa* and *Prevenar 13* in terms of solicited and unsolicited symptoms and serious adverse events (SAEs).
- To assess the neurodevelopmental status of infants born to mothers vaccinated with *Boostrix* during pregnancy or immediately post-delivery, at 9 and 18 months of age.

3.3. Primary endpoint

- Immunogenicity with respect to components of *Infanrix hexa*.
 - Anti-diphtheria, anti-tetanus, anti-HBs, anti-poliovirus type 1, anti-poliovirus type 2, anti-poliovirus type 3 and anti-polyribosyl-ribitol phosphate (anti-PRP) seroprotection status, one month after the booster dose.
 - Booster response to PT, FHA and PRN antigens, one month after the booster dose.

Refer to section 5.3.2 for the definition of the booster response

3.4. Secondary endpoints

- Immunogenicity with respect to components of *Infanrix hexa* and *Prevenar 13*.

Before the booster dose

- Anti-diphtheria, anti-tetanus, anti-poliovirus type 1, anti-poliovirus type 2, anti-poliovirus type 3, anti-HBs and anti-PRP seroprotection status.
- Anti-PT, anti-FHA and anti-PRN and anti-pneumococcal serotypes (1, 3, 4, 5, 6A, 6B, 7F, 9V, 14, 18C, 19A, 19F, 23F) seropositivity rates.
- Anti-diphtheria, anti-tetanus, anti-PT, anti-FHA, anti-PRN, anti-poliovirus type 1, anti-poliovirus type 2, anti-poliovirus type 3, anti-HBs and anti-pneumococcal serotypes (1, 3, 4, 5, 6A, 6B, 7F, 9V, 14, 18C, 19A, 19F, 23F) and anti-PRP antibody concentrations or titres.

One month after the booster dose

- Anti-diphtheria, anti-tetanus, anti-poliovirus type 1, anti-poliovirus type 2, anti-poliovirus type 3, anti-HBs, anti-PRP, anti-PT, anti-FHA, anti-PRN and anti-pneumococcal serotypes (1, 3, 4, 5, 6A, 6B, 7F, 9V, 14, 18C, 19A, 19F, 23F) antibody concentrations or titres.
- Anti-PT, anti-FHA, anti-PRN antibody seropositivity rates.
- Solicited local and general symptoms.
 - Occurrence of solicited local/general symptoms during the 4-day (Day 0-Day 3) follow-up period after booster vaccination.
- Unsolicited adverse events.
 - Occurrence of unsolicited symptoms during the 31-day (Day 0-Day 30) follow-up period after booster vaccination.
- Serious adverse events.
 - Occurrence of reported SAEs from booster dose up to study end.
- Neurodevelopmental status will be assessed at 9 and 18 months of age adjusted for prematurity.
 - Proportion of infants with an ASQ-3 score in the black zone in any domain.
 - Proportion of infants with an ASQ-3 score in the black zone for gross motor skills.
 - Proportion of infants with an ASQ-3 score in the black zone for fine motor skills.
 - Proportion of infants with an ASQ-3 score in the black zone for communication.
 - Proportion of infants with an ASQ-3 score in the black zone for problem solving skills.
 - Proportion of infants with an ASQ-3 score in the black zone for personal-social skills.
 - Proportion of infants referred for formal neurodevelopmental evaluation using BSID-III.

- Proportion of infants with at least one of the indicators of neurodevelopmental impairment using BSID-III.

4. ANALYSIS SETS

4.1. Definition

Four cohorts are defined for the purpose of the analysis:

- Total enrolled cohort
- Total Vaccinated cohort (TVC).
- ATP cohort for analysis of safety
- ATP cohort for analysis of immunogenicity

4.1.1. Total enrolled cohort

The Total enrolled cohort will include all enrolled subjects in the study.

4.1.2. Total vaccinated cohort

The TVC will include all vaccinated subjects for whom data are available.

A safety analysis based on the TVC will include all subjects with booster vaccine administration documented.

- An immunogenicity analysis based on the TVC will include vaccinated subjects for whom data concerning immunogenicity endpoint measures are available.

4.1.3. According-to-protocol cohort for analysis of safety

The ATP cohort for analysis of safety will include all subjects from the TVC who complied with the vaccine administration:

- who have received all vaccine doses in the primary study 201330 [DTPA (BOOSTRIX)-048 PRI].
- who have received the booster dose of study vaccines in the current study.
- for whom administration route and site of study vaccines is known and according to the protocol.
- who have not received a vaccine not specified or forbidden in the protocol.

4.1.4. According-to-protocol cohort for analysis of immunogenicity

The ATP cohort for analysis of immunogenicity will include all evaluable subjects from the ATP cohort for analysis of safety:

- Who meet all eligibility criteria.
- Who received all doses of vaccine in the primary study 201330 [DTPA (BOOSTRIX)-048 PRI].
- Who comply with the procedures and intervals defined in the protocol (refer to Table 5 of the protocol).
- Who do not meet any of the criteria for elimination from an ATP analysis (refer to Section 6.7.2 of the protocol).
- Who did not receive a product leading to elimination from an ATP analysis as listed in Section 6.7.2 of the protocol,
- Who did not present with a medical condition leading to elimination from an ATP analysis as listed in Section 6.8 of the protocol,
- For whom data concerning immunogenicity endpoint measures are available. This will include subjects for whom assay results are available for antibodies against at least one study vaccine antigen component after vaccination.
- The interval between the vaccination visit and post-booster blood sampling, considered for inclusion of a subject will be 21–48 days.

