## 2.2. Secondary objectives

- To assess the persistence of antibodies to all vaccine antigens before the booster dose in infants born to mothers vaccinated with *Boostrix* during pregnancy or immediately post-delivery.
- To assess the immunological response to *Infanrix hexa* and *Prevenar 13* in terms of antibody concentrations or titres against all antigens, one month after the booster dose in infants born to mothers vaccinated with *Boostrix* during pregnancy or immediately post-delivery.
- To assess the immunological response to *Infanrix hexa* in terms of seropositivity rates against pertussis antigens, one month after the booster dose in infants born to mothers vaccinated with *Boostrix* during pregnancy or immediately post-delivery.
- To assess the safety and reactogenicity of *Infanrix hexa* and *Prevenar 13* in terms of solicited and unsolicited symptoms and serious adverse events (SAEs).
- To assess the neurodevelopmental status of infants born to mothers vaccinated with *Boostrix* during pregnancy or immediately post-delivery, at 9 and 18 months of age.

Refer to Section 10.2 for the definition of the secondary endpoints.

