4.1.5. Adapted ATP cohort

When presenting different time points, the Adapted ATP cohort will be used to denote that for each time point, the corresponding ATP cohort for immunogenicity has been used.

More specifically,

- The analyses on the pre and post booster dose time points in mothers, and the cord blood sample will be based on the ATP cohort for immunogenicity in study 116945 (Boostrix-047)
- The analysis on the pre and post primary time points in infants will be based on the ATP cohort for immunogenicity in study 201330 (Boostrix-048).
- The analysis on the pre and post booster time points in infants will be based on the ATP cohort for immunogenicity in study 201334 (Boostrix-049).

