4.2.3. Elimination from ATP cohort for immunogenicity

4.2.3.1. Excluded subjects

All eliminations from the study 201330 [DTPA (BOOSTRIX)-048 PRI] will be applicable for this follow up study except for the visit specific elimination codes (2090, 2100 and 2120).

A subject will be excluded from the ATP cohort immunogenicity under the following conditions

A subject will be excluded from the ATP cohort for immunogenicity when he/she is excluded from the ATP cohort for safety (see Section [4.1.3](#)).

CONFIDENTIAL201334 [DTPA (BOOSTRIX) -049 BST: 048]
Statistical Analysis Plan Final

The following additional codes will be used:

Code	Condition under which the code is used	Visit (timepoints) where the code is applicable	Applicable for analysis set (Safety, immunogenicity)
2010	
Protocol violation (inclusion/exclusion criteria not fulfilled)
 
 Window from DOB to vaccination is 11-18(+30 days) months of age according to the routine national/ local immunization schedule or as specified in the SPM Healthy subjects as established by medical history and clinical examination before entering into the study. Previous booster vaccination against Hib, diphtheria, tetanus, pertussis, pneumococcus, hepatitis B and/or poliovirus since the conclusion visit of study 201330 [DTPA (BOOSTRIX)-048 PRI]. Subjects born to mothers who were vaccinated in 116945 [DTPA (BOOSTRIX)-047] study and having completed their primary vaccination series as per protocol requirement in study 201330 [DTPA (BOOSTRIX)-048 PRI]. 
Also inherited from the 048 study.
	Visit 1/2	Immunogenicity
2040	
Administration of any medication forbidden by the protocol
 
 Administration of immunoglobulins and/or any blood products during the period within three months before the booster dose of study vaccines or planned administration during the study period. 
Also inherited from the 048 study.
	Visit 2/3	Immunogenicity
2050	
Underlying medical condition forbidden by the protocol =>
 
Subjects may be eliminated from the ATP cohort for immunogenicity if, during the study, they incur a condition that has the capability of altering their immune response (e.g. any confirmed or suspected immunosuppressive or immunodeficient condition) or are confirmed to have an alteration of their initial immune status.
 
Also inherited from the 048 study.
	Visit 2/3	Immunogenicity

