2080	
Subjects did not comply with vaccination schedule
 
Inherited from the 048 study.
	Carried forward from previous study	Immunogenicity
2090	
Subjects did not comply with blood sample schedule(date of blood sampling not corresponding to adapted protocol intervals or unknown blood sample date) => 21-48 days from vaccination (Visit 2)
	Visit 3	Immunogenicity
2100	
Serological results not available for antigens POST vaccination (including lost samples, blood sample not done, unable to test, absence of parallelism) => no immunogenicity results available at visit 3.
	Visit 3	Immunogenicity

2120	Obvious incoherence, abnormal serology evolution or error in data (incoherence between CRF and results, wrong sample labelling)	Visit 3	Immunogenicity
------	---	---------	----------------

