5.3. Immunogenicity

5.3.1. Analysis of immunogenicity planned in the protocol

The primary analysis will be based on the ATP cohort for analysis of immunogenicity. If in any vaccine group, the percentage of enrolled subjects excluded from this ATP cohort is more than 5%, a second analysis based on the TVC will be performed to complement the ATP analysis. All analyses will be descriptive.

For each group, at each time point that a blood sample result is available:

- Seropositivity rates against PT, FHA and PRN antigens and pneumococcal antigens (1, 3, 4, 5, 6A, 6B, 7F, 9V, 14, 18C, 19A, 19F, 23F) with exact 95% CI [Clopper, 1934] will be calculated.
- Seroprotection rates against diphtheria toxoid, tetanus toxoid, HBs, PRP antigen and poliovirus types 1, 2, 3 antigens (with exact 95% CI [Clopper, 1934]) will be calculated.
- Percentage of subjects with anti-pneumococcal serotypes (1, 3, 4, 5, 6A, 6B, 7F, 9V, 14, 18C, 19A, 19F, 23F) antibody concentrations, depending on the GSK laboratory or WHO reference laboratory assay cut-offs, will be calculated along with its exact 95% CI [Clopper, 1934].
- Percentage of subjects with anti-D and anti-T antibody concentrations ≥ 1.0 IU/ml will be calculated along with its exact 95% CI [Clopper, 1934].
- Percentage of subjects with anti-PRP antibody concentrations ≥ 1.0 $\mu\text{g/ml}$ and anti-HBs antibody concentrations ≥ 100 mIU/mL will be calculated along with its exact 95% CI [Clopper, 1934].
- GMC/GMT with 95% CI will be tabulated for antibodies against each antigen.
- The booster response rates to PT, FHA and PRN (with exact 95% CI) one month after the booster dose will be calculated.

The above summaries will be provided by country or primary vaccination schedule for countries involving more than 50 subjects.

- The distribution of antibody concentrations/titres for each antigen will be displayed using reverse cumulative distribution curves (RCCs).
- The distribution of antibody concentrations or titres of each antigen will be tabulated.

Handling of missing data:

- For a given subject and a given immunogenicity measurement, missing or non-evaluable measurements will not be replaced. Therefore, an analysis will exclude subjects with missing or non-evaluable measurements.

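### The primary (ATP) analysis of pre-booster antibody persistence is conditioned on a valid, in-window post-booster sample, which has no bearing on serum drawn before the booster

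*SAP*

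**What the plan says.** Persistence heads the list of secondary objectives in protocol 2.2: "To assess the persistence of antibodies to all vaccine antigens before the booster dose in infants born to mothers vaccinated with" Boostrix during pregnancy or just after delivery.

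SAP 4.1.4 (repeating protocol 10.4.4) sets two post-booster conditions for the ATP immunogenicity cohort:
- A result must exist: "assay results are available for antibodies against at least one study vaccine antigen component after vaccination". One antigen is enough.
- The draw must be on time: "The interval between the vaccination visit and post-booster blood sampling, considered for inclusion of a subject will be" 21–48 days. The same section also requires compliance with protocol Table 5, whose footnote 2 independently bars infants seen outside the Visit 2 to Visit 3 interval.

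SAP 4.2.3.1 puts these conditions into practice at subject level: "A subject will be excluded from the ATP cohort immunogenicity under the following conditions". Codes 2090 (draw outside the window), 2100 ("no immunogenicity results available at visit 3") and 2120 (incoherent data, abnormal serological evolution, labelling error) are all listed against Visit 3.

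On the analysis set, SAP 5.3.1 says "The primary analysis will be based on the ATP cohort for analysis of immunogenicity", and applies it "For each group, at each time point that a blood sample result is available". For the pertussis kinetics, SAP 4.1.5 adds: "The analysis on the pre and post booster time points in infants will be based on the ATP cohort for immunogenicity in study 201334". SAP 4.1 defines no separate persistence cohort.

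SAP 5.3.1 also requires a second analysis on the TVC if more than 5% of enrolled subjects in any group fall outside the ATP cohort. Under SAP 4.1.2, the TVC needs vaccination and available immunogenicity data, not a post-booster result.

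**The concern.** The pre-booster sample is taken at Visit 2, before the dose. Nothing at Visit 3 about a month later (a visit on day 50, a lost tube, a failed draw) can make that sample less valid. Yet each of these events removes the infant from the primary persistence estimate.

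This has two costs. Usable data are left out of the headline result for the first secondary objective, and that result is conditioned on later attendance, which is not part of the persistence question.

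The SAP is also not fully consistent here. Sections 4.2.2.1 and 4.2.3.1 describe 2090, 2100 and 2120 as visit-specific and do not carry them over from study 048, so a sampling fault at one visit is not treated as spoiling another. Within this study, the same codes remove the whole subject. Two programmers could reasonably arrive at different pre-booster denominators.

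**Working it through.** **1. Does the post-booster condition reach the pre-booster tables?** SAP 4.1.4 and 4.2.3.1 define membership by subject. SAP 5.3.1 applies that membership at each time point with a blood result, hence before the booster. SAP 4.1.5 says so expressly for the pertussis kinetics. The answer is yes.

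**2. The plan's own figures.** Protocol 10.3 takes up to 340 infants per group and a 20–40% reduction:
- 340 × 0.8 = 272
- 340 × 0.7 = 238
- 340 × 0.6 = 204

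These match Table 16. All 33 of its Clopper–Pearson intervals reproduce to 0.1 point, using a whole-number responder count next to n × rate. For example, 218/272 gives 74.9–84.7.

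**3. When does the TVC analysis run?** The trigger is more than 5% of enrolled subjects in any group. With 340 enrolled, 17/340 = 5.0% does not trigger it and 18/340 = 5.3% does.

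*Not triggered.* At most 17 infants per group are excluded, for all reasons together. At an observed 80%, the exact 95% CI is 75.1–84.1 with n = 323 and 75.3–84.1 with n = 340. The shift in a rate is the discarded fraction × (retained rate − discarded rate). With a fraction of 0.05 and an assumed difference of 10 to 30 points, that is 0.5 to 1.5 points. The mathematical limit is 5 points.

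*Triggered.* The TVC analysis reports the pre-booster samples of vaccinated infants whatever happened at Visit 3. The planned 272, 238 and 204 correspond to 68, 102 and 136 exclusions per group (20%, 30%, 40%), far above 18. Protocol 10.3 describes the reduction as coming from the primary study, however, so part of it may precede enrolment here. The trigger is likely but not certain.

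**4. Gain in the ATP analysis.** The documents do not say how many infants would be excluded for Visit 3 reasons alone. Assume 3–10% of otherwise evaluable infants, and an illustrative 240 per group who satisfy the cohort as written (240 is not a plan figure, but lies within 204–272):
- 240 / 0.97 ≈ 247
- 240 / 0.90 ≈ 267

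| n per group | Responders | Exact 95% CI width (points) |
|---|---|---|
| 240 | 192 | 10.50 |
| 247 | 198 | 10.31 |
| 267 | 214 | 9.91 |

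The reduction is 10.50 − 10.31 = 0.19 to 10.50 − 9.91 = 0.59 points of full width.

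**5. Where there is no fallback.** SAP 5.3.2 limits the subgroup tables (gestational age, maternal age) to the ATP cohort and puts the pertussis analysis across time points, with its evolution graph, on the Adapted ATP cohort. No TVC repeat is stated for either.

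**The case against.** A reader might infer that persistence is analysed solely in infants with a valid Visit 3 sample and that the other pre-booster samples are thrown away. The documents do not support that. The TVC analysis has no post-booster condition and is mandatory above 5% exclusion. Below that level, so few infants are involved that precision hardly changes.

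Three further points favour the plan:
- All analyses are descriptive and the sample size is not power-based, so no decision rule depends on half a point of CI width.
- The documents offer no mechanism or direction linking pre-booster antibody level to Visit 3 attendance. A material bias is therefore possible in principle but not shown.
- One cohort for both time points keeps the pre- and post-booster columns on essentially the same infants, and the rule comes from the protocol.

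These points limit the size of the problem but do not remove it. The TVC analysis is complementary and conditional, and it also readmits infants removed for eligibility violations, forbidden products or wrong administration. No planned table therefore shows all otherwise protocol-compliant infants with a valid pre-booster result. Like-for-like comparison is a real benefit, but booster response, where pairing is essential, already requires both samples in Template 13.

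It is also tempting to say that all three Visit 3 codes should be ignored before the booster. That goes too far for 2120: abnormal evolution is judged across both samples, and a labelling error can concern the pre-booster tube.

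**Conclusion.** The point holds as a minor, inexpensive improvement. The primary persistence analysis depends on a post-booster result and its timing, without a reason that applies to a pre-booster sample. Infants excluded only on that ground reappear, if at all, in the complementary TVC analysis, and no such route is stated for the subgroup tables or the evolution graph.

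The gain is about 0.2–0.6 points of exact 95% CI width at 80%. This rests on the assumed 3–10% loss and the illustrative 240; the true number affected cannot be derived from the documents. The change would also remove the selection on later attendance, whose effect on the estimates is unknown. The primary endpoint is untouched.

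**What to change.** State in SAP 4.1.4, 4.1.5 and 4.2.3 that, for the pre-booster time point:
- codes 2090 and 2100 do not exclude the subject;
- the Visit 2 to Visit 3 interval in protocol Table 5 does not exclude the subject either, since otherwise it would reimpose the same condition by another route;
- all infants who meet the other ATP criteria and have a pre-booster result are included;
- code 2120 continues to remove the pre-booster value unless the error is shown to concern only the Visit 3 sample.

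Booster response continues to require both samples. List the change in SAP section 8, because the cohort is defined in the protocol.

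The cost is a few sentences across those sections. The templates already report N as subjects with available results, so they need no redesign. The downside is that N will differ by time point and the pre- and post-booster columns will not rest on exactly the same infants; a footnote should say so.
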